The proposed, adapted MBTI+ intervention is designed to meet the unique symptom needs of hematologic cancer patients returning home after inpatient chemotherapy. This intervention aims to reduce both insomnia and symptoms of fatigue, pain, and distress. Insomnia is considered a 24-hour disorder, with daytime consequences of nighttime sleeplessness being cited as one of the most upsetting aspects of insomnia. The proposed MBTI+ intervention is innovative in that it integrates training in strategies to address sleep disturbance at night, with training in skills for managing daytime symptoms of daytime fatigue pain and distress. Although the proposed MBTI+ intervention could be beneficial and have implications for improving the health-related quality of life of hematologic cancer patients, to date, MBTI+ has not been adapted for, or tested with this understudied cancer population.

We seek to provide researchers with a better understanding of the feasibility, acceptability, and preliminary efficacy of an adapted MBTI+ protocol for insomnia and daytime fatigue, pain, and distress in patients with hematologic cancer. Given the novel application to this population, it is essential to adapt the protocol to be minimally burdensome (e.g., remote treatment, flexible session scheduling,

and well-received [i.e., high completed sessions, retention, and satisfaction]). If pre- to post-intervention reductions to insomnia symptoms are observed, this would provide support for a larger, more rigorous randomized efficacy trial. Findings could also encourage researchers to extend MBTI+ to other cancer and chronic illness populations reporting insomnia and daytime fatigue, pain, and distress. Finally, positive results could have implications for clinical practice. Patients with hematologic cancer returning home after inpatient chemotherapy might be screened for insomnia, fatigue, pain, and distress, and then offered timely intervention with our MBTI+ protocol. Delivery of this intervention may offset indirect costs associated with insomnia (i.e., physical and psychological comorbidities, health care use, decreased work performance). Future work could assess the cost-effectiveness of the MBTI+ intervention.

Design & Procedures

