Initial feasibility and acceptability of MBTI+ will be assessed with 5 hematologic cancer participants recruited for user testing. Participants will be asked to complete six, 60- to 75-minute intervention sessions with a study therapist. Interventions sessions will be done in-person or via a videoconferencing program (i.e., Zoom), depending on feedback given during focus groups. Participants will be asked to complete daily sleep diaries before each session, and at the beginning of each session participants will be asked several questions about any recent cancer treatments, use of sleep and/or pain medication, and coping skill use. The study sessions will be audio recorded by the therapist using the program Voice Recorder. A subset of these recordings will be reviewed by the study PI and research team to improve the intervention and ensure therapist fidelity to the intervention. Sessions recordings will be stored on a secured drive behind the Duke firewall. These recordings will be destroyed upon study completion. There are three assessments we will ask all participants to complete. They each take about 30-40 minutes and include questions about the participant and their background, their cancer symptoms (e.g., insomnia, fatigue, pain), and their emotions (e.g., symptoms of depression, anxiety, hyperarousal). Participants will also be asked to give feedback on the sessions and intervention content; feedback will be used to make the intervention better for other patients who receive it in the future. The first survey is completed at the start of the study. The second survey is about 7 weeks later and the final survey is about 11 weeks after the start of the study. Study staff will be blinded to outcome assessments, as these will be completed online (i.e., via Redcap). Participants will receive \$40 for completing each of the three study assessments. Total compensation may be up to \$120.

Selection of Subjects

Eligibility criteria for patients included in Phase I and Phase II include:

- 1) an initial or recurrent/relapse diagnosis of acute myeloid leukemia, acute lymphoblastic leukemia, Non-Hodgkin's lymphoma, multiple myeloma, myelodysplastic syndrome
- 2) within 8 weeks of discharge home after inpatient chemotherapy or CAR-T therapy
- 3) score of 8 or greater on the Insomnia Severity Index (ISI);

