Provider recruitment will be facilitated by [name], a hematology-oncologist and member of this study's mentoring committee. [name] will invite his colleagues within the Division of Hematological Malignancies and Cellular Therapy to participate in the provider focus group. Interested providers will be contacted by F32-awardee and study coordinator, [name]. [name] will also deliver a brief presentation about the study to providers within the Division of Hematological Malignancies and Cellular Therapy to advertise the study. Time, format, and location for this presentation will be coordinated with [name].

For patient recruitment, the proposed study will follow the same recruitment procedures used in numerous federally funded projects by our research team in the Duke Pain Prevention and Treatment Research Program (PPTRP).

Under a HIPAA waiver, potentially eligible patients will be identified via electronic medical record review. Potential participants will be emailed directly and/or mailed a letter signed by their treating oncologist and study PI informing them about the study. The email or letter will state that a member of the study team may approach them in clinic at their next appointment; patients wishing not to be approached can call a number to opt out of the study. All study team members who are involved in recruitment ([name]) have completed the required DOCR Recruitment and Engagement training. Confirmation of training completion has been attached to this application. Hematology-oncology providers will be recruited for the focus group directly through [name]. Using a script that is compliant with IRB policies, a member of the study team will describe the study purpose, procedures, risks and benefits, and provide potential participants with an opportunity to ask questions, as well as assess participants' eligibility. Informed consent will be documented by signature on forms approved by the IRB for eligible and interested participants. If a member of the study team is unable to make contact with the participant during a clinic appointment (e.g., due to time constraints, COVID-19 restrictions), the participant will be informed that a member of the study team would like to contact him/her by telephone. In these cases, the eligibility screening and informed consent procedures will occur remotely,

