There are numerous potential benefits of the proposed research. Providers and hematologic cancer patients who participate in the focus group may learn about skills that can help reduce nighttime sleep disturbances and daytime symptoms of fatigue, pain, and psychological stress. Participants who participate in user testing or the single-arm pilot will receive a mindfulness and cognitive-behavioral intervention at no cost. As demonstrated in prior mindfulness and behavioral symptom management studies, the proposed intervention may lead to improvements in patients' nighttime sleep and daytime symptoms of fatigue, pain, and distress. Furthermore, information learned from this study may benefit other patients with cancer in the future. Lessons learned will provide a foundation for subsequent larger, methodologically rigorous, randomized efficacy trials of adapted MBTI. This research program could also serve an heuristic purpose in encouraging researchers to extend adapted MBTI to other cancer and chronic illness populations reporting insomnia and daytime fatigue, pain, and distress. Future work might examine the effects of adapted MBTI on neuroendocrine and immune markers that are linked to sleep and have implications for cancer progression.

Data Analysis & Statistical Considerations

Sample size and statistical power: Part 1 of Phase I will include three focus groups comprised of 4 patients and one provider focus group comprised of 6 medical providers. User testing (Part 2, Phase I) will involve 5 patients. This sample size is based on our prior work using focus groups in the hematology-oncology setting.²⁷ Research suggests that 2-3 focus groups are sufficient to reveal 80% of themes.⁷⁰ If the intervention content is not significantly altered during user testing, these participants will be combined with those from Phase II for an intent-to-treat sample of 35 participants.

Analytic Plan

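### Does the talk of preliminary efficacy in a single-arm pilot need a caveat about untreated change, and a stated confidence interval?

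*Combined protocol and SAP*

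**What the plan says.** Background & Significance states that the study seeks to inform readers about feasibility, acceptability and the "preliminary efficacy of an adapted MBTI+ protocol for insomnia and daytime fatigue, pain, and distress". It continues: "If pre- to post-intervention reductions to insomnia symptoms are observed, this would provide support for a larger, more rigorous randomized efficacy trial". Later in the same paragraph it adds that "positive results could have implications for clinical practice", and describes screening patients and offering them the programme, in conditional wording.

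Phase II is a single-arm pilot of 30 patients (Purpose of the Study). Patients enter "within 8 weeks of discharge home after inpatient chemotherapy or CAR-T therapy" with an ISI of 8 or more (Selection of Subjects). On re-measurement, "The second survey is about 7 weeks later and the final survey is about 11 weeks after the start of the study".

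The Analytic Plan names descriptive statistics for feasibility and acceptability. For the outcomes it names paired t-tests, Cohen's d, unconditional latent growth models over the three assessments, and conditional models with control variables. It names no confidence interval and no significance level. Nowhere does the document say that an uncontrolled change includes whatever would have happened without the intervention.

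**The concern.** Patients are selected on the outcome scale shortly after intensive inpatient treatment and measured again about seven weeks later. Sleep may recover or worsen over that time without any intervention, and selection at a cut-off can add regression to the mean. A fall in mean ISI therefore cannot be attributed to the programme. A reader who meets efficacy language and a remark on clinical practice in one paragraph, with no caveat, could treat the ISI result as early proof of benefit.

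Because the plan gives no significance level or interval, an observed reduction could mean any negative mean change or only a significant one. Recent cancer treatment and days of pain or sleep medication, both recorded at each assessment, could also move the ISI, and the plan does not say they will be shown beside it.

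**Working it through.** **Stated figure.** The only sample-size figure to reproduce is the intent-to-treat number: 30 pilot + 5 user-testing patients = 35. The plan gives no power, SD or target effect for the pilot.

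**Assumptions (not in the documents).** ISI SD 5–6; correlation between baseline and post-treatment 0.6–0.8.

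SD of change = SD × √(2(1 − r)):
- low: 5 × √(2 × 0.2) = 3.16, taken as 3.2
- high: 6 × √(2 × 0.4) = 5.37, taken as 5.4

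**Chance of a favourable result with an inert intervention.** P(mean falls) = Φ(drift × √n / SD of change). P(significant fall) comes from the noncentral t with n − 1 degrees of freedom, two-sided 5% level (also assumed). For 1 point of improvement at n = 30, √30/3.2 = 1.71 and √30/5.4 = 1.01, giving 0.957 and 0.845.

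| Pairs | Untreated drift | Any mean fall | Significant fall |
|---|---|---|---|
| 30 | none | 50% | 2.5% |
| 30 | 1 point better | 85–96% | 16–38% |
| 30 | 2 points better | 98% to >99% | 50–91% |
| 30 | 1 point worse | 4–16% | <1% |
| 24 (20% attrition) | 1 point better | 82–94% | 14–31% |
| 35 | 1 point better | 86–97% | 19–44% |

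So the point is right in principle: modest drift changes the odds. The direction of that drift is not documented. Background & Significance calls the daytime problems persistent and says unhelpful responses can make insomnia worse.

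**Regression to the mean.** Eligibility is assessed first, and "Informed consent will be documented by signature on forms approved by the IRB for eligible and interested participants". The baseline survey is then completed online at study start, so it is a separate measurement from screening. The residual effect is (screening–baseline correlation − r) × (mean of screened-in patients − population mean), with the cut at 7.5 for an integer score of 8. It is zero if baseline and post-treatment correlate equally with screening. At an assumed screening–baseline correlation of 0.9 it is 0.1–0.5 points for a population mean of 14 and 0.3–1.0 points for a mean of 10. It is therefore possible but not established.

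**Confidence interval.** The paired test yields the mean change m and its t statistic, so SE = m/t and the 95% interval is m ± t(0.975, n − 1) × SE. The half-width is t(0.975, n − 1) × SD of change / √n. At n = 30 that is 2.045 × 3.2/√30 = 1.2 to 2.045 × 5.4/√30 = 2.0 points; at n = 24, about 1.3–2.3 points. Any analyst running the planned test has this interval without further specification.

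**What the ISI result is used for.**
- Aim 2 examines outcomes before and after the intervention. Hypothesis 2 expects improvement; neither uses the word efficacy.
- Design & Procedures describes Phase II in the same neutral terms.
- The numerical success criteria are at least 80% of sessions completed, at most 20% attrition, and 80% of participants satisfied. None involves the ISI.
- Benefits says: "Lessons learned will provide a foundation for subsequent larger, methodologically rigorous, randomized efficacy trials of adapted MBTI". That rests the next step on the pilot as a whole.
- The sentence on clinical practice refers to positive results generally, so its link to the ISI change is indirect.

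No rule turns an ISI fall into a decision, and the step named is a randomized comparison.

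**The case for a change.** The best case for acting is that the omission is real and cheap to cure. ISI improvement is a stated hypothesis on the primary outcome. The background cites a large pre-post effect for the original therapy in healthy outpatients with insomnia, so readers will tend to compare this pilot's Cohen's d with it. Leaving definitive efficacy to a later trial does not tell them that the pilot's own early signal cannot be separated from recovery. One sentence would bring the background into line with Aim 2, and a stated interval would show how imprecise the estimate is.

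The facts stand: there is no caveat, no interval is named, and the efficacy phrase is looser than the aim. The need for a change does not. The plan labels the study a single-arm pilot and contrasts it with a more rigorous randomized trial, which concedes the limit. An interval would show sampling error but would not remove drift from the estimate. A table of cancer treatment and medication would not remove it either; those data are already collected, and the conditional models leave room for control variables. A caveat asserting that regression to the mean is present would itself go too far, since the calculation allows zero.

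**Conclusion.** No change is needed. The efficacy phrase is loose background wording, and the unnamed interval is a gap that the planned paired t-test fills as a matter of course. A one-arm pilot that reports change and leaves efficacy to a randomized trial is a fair trade-off at this stage. If drift produced a misleading fall, the consequence named in the plan would be a trial able to expose it.

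The size of the ambiguity depends wholly on assumptions. With 30 pairs and an inert intervention, the chance of a significant fall runs from under 1% (1 point of untreated worsening) to 91% (2 points of untreated improvement, SD of change 3.2). Those figures describe the paired test at an assumed two-sided 5% level; they do not cover the growth models. The conclusion does not depend on where in that range the truth lies, because no criterion, sample size or analysis in the plan turns on the ISI result. It would be different if the plan set an ISI threshold for going ahead or claimed efficacy from this study alone; it does neither.

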Demographic and Medical Variables Collected from Medical Record: These variables will be collected one time when a potential patient is identified for the study under a Waiver of HIPAA authorization. Demographic and medical variables will be collected from electronic medical records (via DEDUCE and Maestro Care) and include the patients' MRN, name, sex, age, marital status, education, race, address, telephone number, cancer type, date of diagnosis, cancer stage, and cancer treatments received. As noted previously, for those who decline, identifying information will immediately be deleted from our records including their address and telephone number. However, we will retain their name and MRN so that we do not contact a person who has already declined participation. We will delete the patient's name and MRN upon completion of enrollment. We will retain demographic information and basic medical information on patients who decline participation in order to see if we are systematically under including certain subgroups of the study population, which would limit our ability to generalize findings. This information will always be kept separate from direct identifiers.

Self-Report Measures. Participants will complete online assessments of primary and secondary outcome measures at all time points (i.e., baseline, post-intervention, 1-month follow-up). These measures have been extensively tested in cancer populations and demonstrate good reliability and validity evidence. We specifically selected measures that are brief to reduce participant burden. Our preliminary data suggests these assessments take a total of 30 minutes to complete.

Primary Outcome. Insomnia. Insomnia symptoms will be measured using the Insomnia Severity Index (ISI).³³ The ISI consists of three items assessing difficulty falling asleep, staying asleep, and waking up too early in the past two weeks. The ISI uses a 5-point response scale, with options ranging from 0 (no difficulty) to 4 (very severe difficulty). The ISI also includes four items assessing satisfaction/dissatisfaction with sleep, how noticeably insomnia is impairing quality of life, distress regarding current sleep disturbance, and interference to daily functioning. The ISI has exhibited good reliability and validity in cancer populations and is recommended for studies targeting insomnia symptoms.

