Secondary Outcomes. Sleep. Sleep will be assessed using the 9-item Whole Week Self-Assessment of Sleep Survey (SASS). This is a retrospective version of the Consensus Sleep Diary from Carney et al. (2012) and includes questions that assess average bedtime, risetime, and sleep quality across the past week (Dietrich, Sethi, Slavish, & Taylor, 2019). **Fatigue.** Fatigue (i.e., severity and interference) will be assessed using the Fatigue Symptom Inventory (FSI), which was developed for and validated in cancer patients. The FSI consists of four items assessing fatigue (worst, least, average, and current fatigue) and seven items assessing fatigue interference in the past week. The FSI includes an 11-point response scale, with options ranging from 0 (no fatigue or no interference) to 10 (fatigue as bad as you can imagine or completely interferences). The FSI is often used in cancer populations and has evidenced excellent reliability and validity. **Pain.** Pain (i.e., severity and interference) will be measured using the Brief Pain Inventory-Short Form (BPI-SF). The BPI-SF consists of four items assessing pain (worst, least, average, and current pain) and seven items assessing pain interference in the past week. The BPI-SF includes an 11-point response scale, with options ranging from 0 (no pain or no interference) to 10 (pain as bad as you can imagine or completely interferes). The BPI-SF has demonstrated good reliability and validity in prior studies investigating pain severity and interference in cancer patients. **Distress. Anxiety and Depressive Symptoms.** Anxiety and depressive symptoms will be measured using the 14-item Hospital Anxiety and Depression Scale (HADS). The HADS consists of two 7-item subscales assessing anxiety and depressive symptoms in the past week. Items are rated using an 4-point response scale. The HADS has demonstrated adequate reliability and validity in cancer populations. **Hyperarousal.** Hyperarousal will be measured using the 16-item Pre-Sleep Arousal Scale (PSAS), which assesses cognitive and somatic arousal before sleep in the past week. The PSAS uses a 5-point scale, with response items ranging from 1 (not at all) to 5 (extremely). The PSAS has demonstrated good reliability and validity in studies targeting insomnia symptoms, and has been used in cancer populations. **Mindfulness.** Mindfulness skills (e.g., observing, describing, etc.) will be measured using the 39-item Kentucky Inventory of Mindfulness Skills (KIMS). Response options range from 1 (never/very rarely true) to 5 (very often/always true). The KIMS has adequate reliability and validity in cancer samples, and has been used in studies exploring mindfulness-based interventions for insomnia. **Self-efficacy for symptom management.** Self-efficacy for symptom management will be measured using the Self-Efficacy for Management Chronic Disease scale. This 6-item scale will assess participants' confidence regarding management of symptoms, medication use, and doctor visits. Response options range from 1 (not at all confidence) to 10 (totally confident). An additional item will be added to assess self-efficacy for managing insomnia. This scale has been shown to have excellent validity and reliability in cancer populations.

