In the proposed study, the risks to participants are minimal and primarily include psychological distress and breach of confidentiality. Participants will be asked about their thoughts and feelings about their cancer; thus, it is possible that they may experience distress. The psychological risk associated with answering questions and participating in the intervention is expected to be minimal. Although some participants may find certain questions or topics to be upsetting, heightened awareness of existing psychosocial and practical needs may be the first step in resolving these concerns. The recruitment letter clearly acknowledges the voluntary nature of participation and patients will have the ability to decline further contact from study personnel (i.e., to opt out). Participants will be fully informed about the study during the informed consent process and instructed to decline to answer any question or to discuss any issues they find troubling. If a participant reports significant distress during study participation, [name] (licensed clinical psychologists) will be consulted. If the participant requires additional treatment, appropriate referrals will be made. The study team has extensive experience conducting psychosocial intervention trials with cancer patients and have not encountered significant psychological distress caused by study participation. Moreover, cancer patients and their family caregivers often report benefits from participating in psychosocial research. Thus, the risk of psychological distress is modest and the safeguards should be adequate. Breach of confidentiality is another possible risk. This is clearly stated in the consent form. All efforts will be made to maintain confidentiality. Participants' data and research records will be carefully stored. All study personnel will be required to complete courses and ongoing training in protecting participant confidentiality.

The adapted MBTI intervention involves sleep consolidation and reconditioning exercises. Although unexpected, it is possible that these sleep strategies may result in increased daytime sleepiness, and some problems with mood and/or slowed thinking during treatment; however, these effects are primarily restricted to the early stages of treatment, when behavioral therapies are introduced, and improve over time, typically resolving by the end of treatment.

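### No systematic question is described for the early side effects that the plan itself names (sleepiness, mood problems, slowed thinking), so the pilot as described yields no count of them

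*Combined protocol and SAP*

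**What the plan says.** All references are to the combined protocol and SAP.

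- **The effects.** Risk/Benefit Assessment, Risks: "Although unexpected, it is possible that these sleep strategies may result in increased daytime sleepiness, and some problems with mood and/or slowed thinking". The same sentence describes them as "primarily restricted to the early stages of treatment, when behavioral therapies are introduced, and improve over time, typically resolving by the end of treatment".
- **Survey times.** Phase I: User Testing and Phase II: Single Arm Pilot: the first survey is at the start, then "The second survey is about 7 weeks later and the final survey is about 11 weeks after the start of the study".
- **Recall periods.** In the self-report measures, the ISI asks about "difficulty falling asleep, staying asleep, and waking up too early in the past two weeks". The SASS, FSI, BPI-SF, HADS and PSAS each refer to the past week; for example, "The HADS consists of two 7-item subscales assessing anxiety and depressive symptoms in the past week".
- **During treatment.** At the start of each session, "participants will be asked several questions about any recent cancer treatments, use of sleep and/or pain medication, and coping skill use". At sessions 3 and 6 the therapist also records skills practice and homework in RedCap (Treatment Feasibility and Acceptability). Daily sleep diaries are completed before each session, but their items are not listed.
- **Other channels.** "Participants will also be asked to give feedback on the sessions and intervention content". On the audio recordings: "A subset of these recordings will be reviewed by the study PI and research team to improve the intervention". A participant who reports significant distress triggers a psychologist consultation and, if needed, referral (Risks).
- **Data & Safety Monitoring.** The data sources named are chart review, focus groups and self-report inventories. No adverse-effect form, definition or count is described.

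**The concern.** The plan predicts effects that appear early and are gone by the end of treatment. It then describes structured symptom measurement only before treatment and at or after its end. If the effects behave as predicted, they fall between the surveys.

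What is at stake is a simple tolerability record: how many participants had each effect, at which session, how strongly, and whether it passed. The plan has two uses for such a record.

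- User testing in five patients is meant to refine the timing, scaling and content of the intervention (Purpose of the Study). For these effects it would rest on unsystematic impressions.
- The pilot is meant to support larger randomised trials (Benefits), whose side-effect monitoring would need these figures.

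The Background notes that MBTI has been tested only in otherwise healthy outpatients with insomnia. Tolerability in patients within 8 weeks of discharge is therefore not yet known. Asking at each session would also give a set point for referring a participant who is getting worse.

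**Working it through.** The plan states no figure on this point, so there is none to reproduce. The check compares when the effects are expected with when anything asks about them.

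**1. Reach of the surveys.** Inputs: surveys at about weeks 0, 7 and 11; recall of two weeks (ISI) or one week (the other measures with stated recall).
- ISI at week 7 reaches back to 7 − 2 = week 5. The one-week measures reach back to 7 − 1 = week 6.
- So 5/7 = 71% (ISI) to 6/7 = 86% (one-week measures) of the time between the first two surveys lies outside the recall window.

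**2. Weeks on the strategies that are missed.** Session spacing and the session that introduces the strategies are not stated. Assume weekly sessions at weeks 1 to 6 and strategies from session s. The weeks before the recall window are 5 − s for the ISI and 6 − s for the one-week measures.

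| Strategies start at session | ISI | One-week measures |
|---|---|---|
| 1 | 4 | 5 |
| 2 | 3 | 4 |
| 3 | 2 | 3 |

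**3. Content.** No listed measure is described as assessing sleepiness or slowed thinking. The nearest are FSI fatigue and the ISI item on interference with daily functioning. HADS and FSI at weeks 7 and 11 can show mood or fatigue problems that persist, but not ones that came and went.

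**4. What systematic asking could deliver.** The true rates are assumed, since the documents give none.
- At least one case among 35 at a rate of 10%: 1 − 0.9^35 = 97.5%.
- At least one case among the 5 user testers at a rate of 20%: 1 − 0.8^5 = 67%.
- No cases among 35: one-sided 95% upper bound 1 − 0.05^(1/35) = 8.2%.
- 7 cases among 35: exact (Clopper-Pearson) 95% CI 8.4% to 36.9%, for reports from any cause.

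**5. How not to define an affected participant.** A no-change simulation used 200,000 persons, integer ratings from 0 to 10 with mean 4, independent sessions, one reference rating and five later ones, on one item. The session-to-session SD is assumed. The table gives the share flagged although nothing changed.

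| Rule | SD 1.0 | SD 1.5 | SD 2.0 |
|---|---|---|---|
| Any rise | 70% | 75% | 77% |
| Rise of 3 or more | 14% | 34% | 47% |
| Rise of 4 or more | 3% | 17% | 31% |
| Rise of 3 or more, two sessions running | 3% | 10% | 18% |

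For a 4-point rise, 3% to 31% is about 1 to 11 of 35 participants. With three independent items, the share flagged on at least one is 1 − (1 − 0.03)^3 = 9% to 1 − (1 − 0.31)^3 = 67%. There is also a ceiling: from a starting rating of 7 or more on a 0-10 scale, a 4-point rise is impossible.

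**The case against.** **Existing contact.** Participants have six one-to-one sessions of 60 to 75 minutes, so a therapist sees each of them repeatedly in the early period. Sessions are recorded, feedback is requested, and psychologist consultation is available. The exclusion criteria also remove cognitive impairment, narcolepsy, seizure disorder and serious psychiatric conditions where these meet the stated conditions. This stands as far as individual cases go: a troubled participant may well be noticed. It does not give a count, because no recording or tabulation rule is described.

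**Undescribed content.** The diary items and feedback questions are not listed, and the session-start questions are only summarised. A reader might infer that the effects would certainly go uncounted. The documents do not support that. They show only that no such question is described. Feedback has no stated recall limit and could reach back to early sessions.

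**Not an aim.** The aims are feasibility, acceptability and pre-post outcomes in a minimal-risk pilot, and the plan calls these effects unexpected. This stands, and it limits the point to a cheap improvement. A reader might also infer that the efficacy or feasibility results are compromised; nothing in the documents suggests so.

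**Weak data.** Any figure would be uncontrolled. Entry requires fatigue, pain or distress of 5 or more, so complaints from other causes are likely, and thresholds on rises are noisy. This too stands. It argues for descriptive reporting and against a fixed rise as the only definition, but not against asking. With five user testers, an effect present in 20% has a 33% chance of appearing in none, so their answers can inform refinement but cannot rule an effect out.

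**Conclusion.** The point holds as a modest improvement. The plan names three possible early effects and describes no systematic question about them for the period in which it expects them. As described, it produces no count and provides a response only to reported significant distress.

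The reach of the surveys follows from the stated, approximate survey times and applies only to instruments with a stated recall period. The estimate of 2 to 5 missed weeks on the strategies also assumes weekly sessions and a start at session 1, 2 or 3. The detection figures rest on assumed rates, and the noise figures on assumed SDs, a mean of 4 and independent sessions. None of these assumptions is needed for the main conclusion. The diary forms or feedback questions, once seen, could narrow the gap.

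**What to change.** 1. Add a short checklist to the existing session-start questions: daytime sleepiness, mood problems and slowed thinking since the last session (past week at session 1), each as present or not, with severity 0-10. Start before the sleep strategies are introduced. The therapist records it in RedCap, as for the engagement data.
2. Set in advance a severity level that leads to referral (PI, treating oncologist or consulting psychologists).
3. Record the reason for each withdrawal.
4. Under Aim 2, using the descriptive statistics already planned, report by session how many participants describe each effect as new or worse than before the strategies, its peak severity, and whether it had resolved by session 6. Ask for new or worse directly. Do not rely on a fixed 3- or 4-point rise as the only definition.
5. State that the figures are uncontrolled and not attributable to the intervention.
6. Review the five user testers' answers before the pilot begins.

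**Cost.** Three items × six sessions × 35 participants = at most 630 item responses, plus a few RedCap fields, a short addition to Aim 2 and an IRB wording amendment. No new visit or staff is needed. The downsides are an assumed one to two minutes per session, and direct asking may raise reports of mild symptoms.
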